**Table 4. Group 2 Allowable Schedule**

Study Visit	Should occur	May occur
Visit 0 (screening and consent)	On or before D0	Within 2 weeks of visit 1
Visit 1 (eligibility, blood draw, MMR vaccination)	Day 0	on Day 0
Visit 2 (MMR follow-up)	Day 2	2 to 5 days after MMR vaccination
Visit 3 (MMR follow-up)	Day 14	14 to 17 days after MMR vaccination
Visit 4 (MMR follow-up)	Day 28	28 to 35 days after MMR vaccination
Visit 5 (MMR blood draw, CD-JEV vaccination)	Day 56	56 to 63 days after MMR vaccination
Visit 6 (CD-JEV follow-up)	Day 58	2 to 5 day after CD-JEV vaccination
Visit 7 (CD-JEV follow-up)	Day 70	14 to 17 days after CD-JEV vaccination
Visit 8 (CD-JEV blood draw, MMR vaccination)	Day 84	28 to 35 days after CD-JEV vaccination
Visit 9 (MMR follow-up)	Day 86	2 to 5 days after MMR vaccination
Visit 10 (MMR follow-up)	Day 98	14 to 17 days after MMR vaccination
Visit 11 (final assessment)	Day 112	28 to 35 days after MMR vaccination

## **8. STUDY PROCEDURES/EVALUATIONS**

### **8.1. Clinical Evaluations**

A key objective of this study is to describe the safety profile of the study vaccines. AEs and SAEs are defined in Section 9. Included below are brief listings of clinical parameters to be measured and used in evaluation of the general health of the child and in describing safety of study vaccines.

#### **8.1.1. Medical History**

At enrollment, medical histories will be reviewed through interview with the participant and his/her parent/legal guardian. The following medical conditions, especially, will be assessed:

- Current or recent febrile illness
- Recent vaccination history
- Hypersensitivity of any kind
- Any chronic disease (cardiac, renal, neurologic, metabolic, or rheumatologic)
- Seizures, including history of febrile seizures, or any other neurologic disorder

#### **8.1.2. Physical Examination**

Qualified study staff will collect general information on the participant including:

- Recording of general participant appearance
- Measurement of height and weight
- Measurement of the following vital signs:
  - Body temperature (and body location of measurement)
  - Respiratory rate
  - Pulse rate/heart rate

Qualified study staff will conduct a physical examination of all participants. This physical examination will include the following:

- Physical examination of all organ systems. This includes, without limitation, the following:
  - Chest auscultation
  - Heart auscultation
  - Abdomen palpation

### **8.1.3. Specific Clinical Signs and Symptoms of Interest**

During follow-up, all clinical signs and symptoms must be documented. However, the following signs and symptoms and date of onset/occurrence and resolution will be solicited and recorded for all participants from 30 minutes until 14 days post vaccination per section 9.2.3.1. Signs and symptoms to be solicited will be those commonly reported in the large cumulative experience of CD-JEV and MMR in children.

Local Signs/Symptoms at the Injection Site:

- Ecchymosis (bruising)
- Erythema (redness)
- Edema (swelling)
- Induration (hardness)
- Pain/tenderness

General Signs/Symptoms:

- Fever
- Rash
- Cough
- Runny nose
- Change in eating habits
- Diarrhea
- Sleepiness
- Irritability
- Unusual crying
- Vomiting

In addition, a standardized clinical assessment including history and physical examination will be conducted by all clinicians per routine community practice. Evaluation of the above solicited signs/symptoms and unsolicited adverse events will include assessment of severity per Section 9.2.1.

Reported symptoms and clinical signs will be recorded in a daily diary by parent/guardian. Evaluations will be made by qualified study staff on each day of visit to the study clinic (Group 1: Days 0, 14, 28, 56, 84, 98, 112; Group 2: Days 0, 14, 28, 56, 70, 84, 98, 112) and at any time a participant is seen by a clinician.

Parents will be instructed to complete a daily diary of the above Specific Clinical Signs and Symptoms of Interest to the best of their ability. Parents will be instructed to contact a study clinician in the event of illness that may require urgent care to facilitate a rapid assessment of danger signs and assist in arranging transportation by the study to the health center or local hospital, as required. While the event may or may not be attributable to the study vaccines, study staff will follow the ethical imperative of

assisting ill participants once aware of severe illness. After referral, it will be the responsibility of a study clinician to assess and document all signs and symptoms.

#### **8.1.4. Illness Diagnosis and Treatment**

Participants will be instructed to seek care at the study sites and referred to RITM when necessary. The care provided to study participants presenting for outpatient consultation services at the sites will be recorded directly to the subject medical record. For participants visiting sites during non-working RITM hours, hospitalized at RITM, or visiting another facility, the study team will request the medical abstract. In the event this information cannot be obtained from the facility, as much information as possible will be obtained from the family of the participant. If the event is classified as an SAE, medical records regarding the event must be obtained.

While parents will be encouraged to seek care for their child at the sites or RITM, for participants presenting to a health center or transported to a health center or hospital other than RITM, a clinical assessment will be performed by a non-study health practitioner per routine community practice. Data on participant illness history, physical examination, diagnosis, and treatment will be documented. If necessary, staff will assist in arranging transportation for higher level care if necessary in their clinical judgment.

## **8.2. Laboratory Evaluations**

### **8.2.1. Clinical Laboratory Evaluations**

There will be no clinical (safety) laboratory evaluations scheduled in this study. However, laboratory testing will be provided if required for the assessment of an AE. Laboratory assays specified in Section 8.2.2. are for research purposes only and are not to be used for clinical diagnosis.

### **8.2.2. Serum Assays**

#### **8.2.2.1. Anti-Japanese Encephalitis Immunogenicity Testing**

JE vaccine immunogenicity will be assessed by measurement of serum anti-JE neutralizing antibody. Testing will be performed at the Department of Virology, Armed Forces Research Institute of Medical Sciences in Bangkok, Thailand. A 50% PRNT will be used to measure neutralizing antibodies for JE. Seroprotection will be defined as a serum JE PRNT titer of  $\geq 1:10$ .

#### **8.2.2.2. Measles**

Measles vaccine immunogenicity will be assessed by measurement of serum anti-measles neutralizing antibody. Testing will be performed at the Laboratory of Pediatric and Respiratory Viral Diseases, US FDA, in [name]. A 50% PRNT will be used to measure neutralizing antibodies for measles virus. Seroprotection will be defined as a serum measles plaque reduction neutralization concentration of  $\geq 120$  mIU/mL, as measured by the PRNT (dilution converted to concentration using the 3rd International Standard Reference serum).

### **8.2.2.3. Mumps**

Mumps vaccine immunogenicity will be assessed by the presence of serum anti-mumps IgG antibody. Testing will be performed at the Laboratory of Pediatric and Respiratory Viral Diseases, US FDA, in [name]. A commercial IgG ELISA will be used to measure anti-mumps IgG antibody. Seroprotection will be defined as a serum anti-mumps IgG OD ratio  $\geq 1.10$  per the package insert.

### **8.2.2.4. Rubella**

Rubella vaccine immunogenicity will be assessed by measurement of serum anti-rubella IgG concentration. Testing will be performed at the Laboratory of Pediatric and Respiratory Viral Diseases, US FDA, in [name]. A commercial IgG ELISA will be used to measure anti-rubella antibody concentration. Seroprotection will be defined as a serum anti-rubella IgG concentration corresponding to  $\geq 10$  IU/mL per the package insert.

## **8.2.3. Specimen Preparation, Handling, and Shipping**

### **8.2.3.1. Specimen Collection**

Blood draws of 3-5 mL will be collected during study visits as outlined in Section 7. The identity of the child will be verified immediately prior to the blood draw using the child's study participant number. Aliquot labels will be generated that indicate the participant ID, a designation for the type of test required (MMR and/or JE), and timepoint of collection (pre or post). One label will be affixed onto the vacutainer tube immediately following the blood sample drawing.

After collection, blood samples must clot for 60 minutes to 2 hours at room temperature. Samples will be maintained at 2°C to 8°C until processed in the site laboratory.

### **8.2.3.2. Specimen Preparation, Handling, and Storage**

After centrifugation, the serum will be aliquoted. To ensure that samples are not mixed or inaccurately labelled, the child's study participant number, date of blood collection, number of aliquots obtained, and the date and time of aliquoting will be specified on the sample identification log. Comments may be made on the quality of samples (e.g., hemolyzed, contaminated). A label will be affixed onto each of the aliquots to indicate participant ID, a designation for the type of test required (MMR or JE), and timepoint of collection (pre or post).

All serum aliquots will be kept under appropriate conditions at the local study site. Study staff will monitor and record temperature on the appropriate form during the entire trial. For anti-JE testing, serum aliquots collected on D0 and D28 for Group 1 and D56 and D84 for Group 2 will be shipped to the Department of Virology, Armed Forces Research Institute of Medical Sciences in Bangkok, Thailand. For anti-measles, anti-mumps, and anti-rubella testing, serum aliquots obtained on D0 and D56 for both groups will be shipped to the Laboratory of Pediatric and Respiratory Viral Diseases, US FDA, in [name]. A backup aliquot from each timepoint of collection will be retained for five years following study completion. Only authorized study staff will have access to the samples.

### **8.2.3.3. Specimen Shipment**

Specimens will be shipped according to the International Air Transport Association regulations. Following the testing of specimens, all remaining back-up specimens will be stored for five years at a location designated by the sponsor following study completion.

## **9. ASSESSMENT OF SAFETY**

### **9.1. Specification of Safety Parameters**

Study vaccine safety profiles will be parameterized as the proportion of participants experiencing specific adverse events categorized into one of the following categories:

- Immediate reactions occurring within 30 minutes of administration of each study vaccine, as observed by study staff or reported by the participant to study staff.
- Solicited signs and symptoms occurring greater than 30 minutes after administration of each study vaccine through 14 days following vaccination, as observed by the parent/guardian and indicated on the diary card or observed by study staff.
- All other adverse events occurring within 28 days of receipt of each study vaccine, as observed by study staff or reported by the participant's parents to study staff.
- All SAEs occurring during the course of the study, as observed by study staff or reported by the participant's parents to study staff.

### **9.2. Methods and Timing for Assessing, Recording, and Analyzing Safety Parameters**

#### **9.2.1. Adverse Events**

An adverse event is defined as any untoward medical occurrence in a patient or clinical investigation participant administered a pharmaceutical product, which does not necessarily have a causal relationship with this treatment. An AE can therefore be any unfavorable and unintended sign (including an abnormal laboratory finding), symptom, or disease temporally associated with the use of a medicinal product, whether or not considered related to the medicinal product. The occurrence of an AE may come to the attention of study personnel during study visits and interviews of a study participant presenting for medical care.

Information to be collected on adverse events includes event description, date of onset, clinician's assessment of severity, relationship to study product (assessed only by those with the training and authority to make a diagnosis), and date of resolution/stabilization of the event.

Any medical condition that was present at the time that the patient was enrolled should not be reported as an AE. However, if it deteriorates during the study safety recording periods, it should be recorded as an AE.

AEs should be graded for severity and relationship to vaccine.

**Severity of Event:** Any AE which is not a local and systemic sign or symptom occurring within 14 days of vaccination will be assessed to quantify intensity using the following guidelines:

Grade	Categorization	Definition
Grade 1	Mild	Symptoms causing no or minimal interference with usual social & functional activities with intervention not indicated
Grade 2	Moderate	Symptoms causing greater than minimal interference with usual social & functional activities with intervention indicated.
Grade 3	Severe	Symptoms causing inability to perform usual social & functional activities with intervention or hospitalization indicated.
Grade 4	Potentially life-threatening	Symptoms causing inability to perform basic self-care functions with intervention indicated to prevent permanent impairment, persistent disability, or death.

*\*Intervention defined as medical, surgical, or other procedures recommended or provided by a healthcare professional for the treatment of an adverse event.*

Changes in the severity of an AE should be documented to allow an assessment of the duration of the event at each level of intensity to be performed. Adverse events characterized as intermittent require documentation of onset and duration of each episode.

**Relationship to Study Vaccines:** The clinician's assessment of an AE's relationship to test vaccine is part of the documentation process, but it is not a factor in determining what is or is not recorded in the study. If there is any doubt as to whether a clinical observation is an AE, the event should be recorded. All AEs must have their relationship to study vaccines assessed using the following guidelines:

Categorization	Definition
Definitely Related	An adverse event or unanticipated problem clearly related to the research procedures.
Possibly Related	There is a reasonable possibility that the adverse event or unanticipated problem, incident, experience, or outcome may have been caused by the procedures involved in the research.
Not Related	Any adverse event or unanticipated problem clearly not related to study procedures.

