### **9.2.3. Reactogenicity**

Reactogenicity post-vaccination will be assessed from 30 minutes through 14 days following vaccination. All solicited local and systemic signs recorded from 30 minutes through 14 days post vaccination will be considered “related” to study vaccination. The parent will use a structured reactogenicity diary card for recording solicited (pre-listed) and unsolicited reactogenicity. Any reactogenicity continuing beyond 14 days will be documented as an adverse event and followed until resolution.

Any reactogenicity will be managed in accordance with good medical practices by the clinical study site team who will assess and treat or refer the child for medical care as appropriate. If needed to monitor or treat reactogenicity, additional study visits may be conducted. If any acute treatment or medical care is required as a result of harm caused by the study vaccine or study procedure, this care will be provided by the site free of charge. All children reporting reactogenicity will be followed clinically until the condition resolves (returns to baseline) or stabilizes. Conditions likely to be related to the product, whether serious or not, which persist at the end of the trial will be followed up by the study clinician until resolution or stabilization.

The parents of infants enrolled in this study will be instructed to contact the study site staff to report any reactogenicity of concern that their child experiences. In the case of a life-threatening event, they will be instructed to seek immediate emergency care. Where feasible and medically appropriate, parents will be encouraged to seek medical care for the child at the RITM clinic, and to request that the study physician be contacted upon their arrival.

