#### **9.2.4. Serious Adverse Events**

An SAE is defined as an AE that meets one of the following conditions:

- Death.
- Life threatening (participant at immediate risk of death) (*The term “life-threatening” in the definition of “serious” refers to an event in which the patient was at risk of death at the time of the event; it does not refer to an event which hypothetically might have caused death if it were more severe*).
- Requires inpatient hospitalization or prolongation of existing hospitalization.
- Results in a persistent or significant disability or incapacity.
- Important medical events that may not result in death, be life threatening, or require hospitalization may be considered SAEs when, based upon appropriate medical judgment, they may jeopardize the participant and may require medical or surgical intervention to prevent one of the outcomes listed in this definition. Medical and scientific judgment should be exercised in deciding whether reporting is appropriate.

All SAEs occurring at any time during the study must be reviewed and evaluated by a study clinician (SAE relationship to study vaccine must be evaluated as outlined in Section 9.2.1) and recorded on an SAE form and reported (as specified in Section 9.3). All SAEs should be followed until satisfactory resolution or until the study clinician deems the event to be chronic or the patient to be stable.

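### Protocol 9.2.1 asks for each adverse event's relationship to the vaccines but defines all three causality categories against procedures, so read literally a harm caused only by the blood draw cannot be graded Not Related

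*Protocol*

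**What the plan says.** Protocol 9.2.1 sets the question twice: "AEs should be graded for severity and relationship to vaccine", and "All AEs must have their relationship to study vaccines assessed using the following guidelines". Those guidelines are a three-row table:

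- Definitely Related: "An adverse event or unanticipated problem clearly related to the research procedures".
- Possibly Related: a reasonable possibility that the event "may have been caused by the procedures involved in the research".
- Not Related: "Any adverse event or unanticipated problem clearly not related to study procedures".

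Protocol 9.2.4 sends serious events to the same scale: "SAE relationship to study vaccine must be evaluated as outlined in Section 9.2.1". SAP 7.2 repeats the unsolicited AE and SAE summaries for events found to be related to the vaccination. The SAP does not redefine the scale and does not say which categories count as related.

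**The concern.** The question is about the vaccine, but the answers are worded about procedures, and in this trial the two are not the same. Each infant has three blood draws, and Protocol 2.3.1 lists discomfort and, rarely, infection at the draw site as possible harms. If an assessor follows the written definitions, a harm due only to the draw is graded as related and then reported as related to vaccination.

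Describing the vaccines' safety is a secondary objective, and the related-AE and related-SAE summaries are where a reader looks for events attributed to vaccine. In a sparse related-SAE table even one misattributed event could be misread. Two assessors could also grade the same event differently and both cite 9.2.1.

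**Working it through.** There is no plan figure to reproduce. The check compares texts and then counts blood draws.

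**1. Does *procedures* include the blood draw?** Protocol 8.2.1 says of the assays that the draws supply: "Laboratory assays specified in Section 8.2.2. are for research purposes only and are not to be used for clinical diagnosis". Drawing blood for them is therefore a research procedure. Protocol 9.2.3 refers to "harm caused by the study vaccine or study procedure", which names vaccine and procedure as separate sources of harm. *Procedures* in the table cannot fairly be read as the vaccine alone.

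**2. Apply the definitions to an infection caused only by venipuncture.**

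| Category | What the wording requires | Met? |
|---|---|---|
| Definitely Related | clear link to research procedures | yes, in a clear case |
| Possibly Related | reasonable possibility of a procedural cause | yes, in a doubtful case |
| Not Related | clearly no link to study procedures | no |

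There is no separate category for procedure-related events.

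**3. Follow the rating into the tables.** Solicited local reactions in 9.2.3.1 are those at the injection site, so a draw-site infection is not on that list and goes through the 9.2.1 scale. The SAP does not map the categories, but an event graded Definitely Related counts as related under any mapping. Solicited reactions are unaffected, because 9.2.3 treats them as related by rule.

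**4. Count draws in each reporting window.** The inputs are the draw days and vaccination days in Protocol 4 and 7.14 and the 28-day window in SAP 7.1.

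- Group 1: draws on Days 0, 28(+7) and 56(+7). MMR and CD-JEV on Day 0, second MMR on Day 84(+7).
- Group 2: draws on Days 0, 56(+7) and 84(+7). MMR on Day 0, CD-JEV on Day 56(+7), second MMR 28 to 35 days after CD-JEV.

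| Table | Group 1 draws clearly inside | Group 2 draws clearly inside |
|---|---|---|
| 28 days after first MMR | 1 (Day 0) | 1 (Day 0) |
| 28 days after CD-JEV | 1 (Day 0) | 1 (Day 56) |
| 28 days after second MMR | 0 | 1 (Day 84) |
| SAEs, whole study | 3 | 3 |

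Two draws are borderline because they fall 28 to 35 days after a vaccine: Group 1 Day 28 (first MMR and CD-JEV windows) and Group 2 Day 84 (CD-JEV window). An event starting after such a draw is inside the window only if the draw is on day 28 and onset is the same day. Group 1's Day 56 draw is in no window.

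For SAEs, planned draws are 314 × 3 = 942 per arm and 942 × 2 = 1,884 in all, a difference of 0. These are counts of draws, not of events. The documents give no rate of venipuncture events, so they cannot be turned into an expected number.

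**The case against.** The strongest reply is that the intended meaning is plain. The heading and lead-in to the table, the rest of 9.2.1, Protocol 4, Protocol 9.2.4 and SAP 7.2 all name the vaccine or vaccination as the target. Only people with the training and authority to diagnose may judge causality (9.2.1). The investigator or a designee reviews the assessments (Protocol 15.1), every SAE goes to the medical monitor within 24 hours (9.3.1), and the safety monitoring committee reviews all SAEs against what is known or expected of the vaccine (9.5.2). The participant-level listings would expose a draw-site event. Any error would also be toward attributing too much to the vaccine, so no vaccine harm is hidden.

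Most of this stands, and it is why the effect is small. It does not correct the definitions. Assessors are told to use the table, and correct grading then depends on departing from its words.

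A reader might also infer a bias between arms, because all three Group 2 draws fall on vaccination visits and only one of Group 1's does. The documents do not support that. SAP 7.1 reports events for each vaccination separately, and on that basis the only clear difference is 0 v 1 after the second MMR, when both arms receive MMR alone. That visit does not bear on concurrent versus separate administration.

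**Conclusion.** The point holds as a minor wording error. The causality definitions are broader than the question they answer, and an unsolicited AE or SAE caused only by the blood draw cannot be Not Related if they are followed literally.

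A reader might go further and infer that the related-event tables will be materially wrong. The documents do not support that. The text around the table directs assessors to the vaccine, several layers of review follow, and Protocol 2.3.1 calls draw-site infection rare and ties it to improper technique. The consequence is confined to descriptive safety summaries. The measles and rubella primary endpoints are untouched, and no bias in the comparison of arms is claimed.

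The conclusion rests on two assumptions: that the blood draw is a study procedure, which 8.2.1 and 9.2.3 support, and that the 9.2.1 rating feeds the SAP 7.2 summaries, since neither document defines another scale.

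**What to change.** In the 9.2.1 table, replace the three references to procedures with *study vaccine(s) or their administration (injection)*. Naming the injection keeps events due to injection technique, such as an abscess from a contaminated injection, within related, in line with the SAP's wording about vaccination. Events caused only by the blood draw then become Not Related.

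That change alone would stop the protocol's only causality scale from flagging procedure harm. So instruct assessors to note a procedural cause in the event description, which 9.2.1 already collects. In SAP 7.2, state that the related-AE and related-SAE summaries use this rating.

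The cost is three phrases in one protocol table, a short instruction to assessors and one SAP sentence. No visit, staff or eCRF item is added. No event is lost, because 9.2.1 says that the relationship judgement does not decide what is recorded.
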